d. Duration of an individual subject's participation in the study and the time involved:

The patients will be participating in the study for as long as the epidural catheter remains in place for clinical indications. The expected time will be between 6 and 12 hours.

7. Data and Specimen Management

a. Data analysis plan:

Sample size: Based on previous experiences for a measurable difference of 0,5 cm, we will include 35 patients in each group to have a power of 90% and a statistical significance level of 0,05. Data will be analyzed using analysis of variance, Student's t test, chi-square test and Pearson's correlation coefficients where appropriate.

N/A

b. Power analysis:

See above

N/A

c. Data handling:

N/A

i. Information included in the data

Following dressing application, demographic variables of each patient will be recorded including (age, gravity, parity, weeks of gestation, weight, height, BMI). Other recorded variables include time of insertion, distance from catheter tip to skin in centimeters. One hour after delivery, immediately before catheter removal, time, duration of catheter presence, centimeters from skin to catheter tip and dressing integrity will be recorded. Dermatomal level and symmetry of the block will be recorded every two hours or every time the patients requires a top-up dose. We will also record number of top up doses and rate of epidural infusion as well as the need for catheter replacement during the observation period.

Primary outcomes

Epidural catheter migration (ECM) in centimeters = Distance from tip to skin at insertion - Distance from tip to skin at removal. If the catheter moves inward, ECM will be negative and if it gets displaced outwardly, ECM will be positive.

Secondary outcomes

- 1) Dermatomal sensory level measured with thermal discrimination
- 2) Incidence of asymmetric block
- 3) Rate of epidural catheter replacement
- 4) Total epidural dose (mL)
- 5) Number of top-up epidural boluses.

ii. Data storage

Data derived from the study will be stored in a locked drawer in the office of the PI for the duration of the study. The de-identified information will be accessed by the research team and the statistician for analysis.

iii. Duration of data storage

For one year after study completion.

iv. Access to data

The PI and the research team.

v. Responsible for receipt or transmission of the data

The Principal Investigator

vi. Data transport

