From the site of data collection to the PI office by the Principal Investigator.

8. Provisions to Monitor the Data to Ensure the Safety of Subjects

a. Data safety and delivery plan

The Principal Investigator (PI) will be responsible for the conduct of this study, including overseeing participant confidentiality, executing the Data and safety Monitoring (DSM) plan, and complying with all reporting requirements to local and federal authorities. This oversight will be accomplished through additional oversight from a Data and Safety Monitoring Committee at the Augusta University. We will conduct ongoing review of all serious adverse events (SAEs), unanticipated problems (UAPs) and reportable adverse events (AEs). Per the DSM Plan, SAEs, UAPs and reportable AEs will be reported to the institutional committee and IRB per study protocol. All SAEs, UAPs and reportable AEs are to be reported to the committee and IRB within 5 business days of receiving notification of the occurrence.

Audits will consist of a review of the regulatory documents, consent forms, and source data verification. Results and recommendations from audits will then need to be submitted by the PI to the IRB of record at the time of the continuing review.

b. Data review.

We will review the results for analysis at the end of data collection. The participants will be informed from the beginning of the study that any concerns related to the study be communicated directly to the PI, who will address them according to the DSM plan.

c. Collection of safety information

Data will be de-identified right after collection and be kept as paper record in the PI office.

d. Frequency of data collection

Data will be collected daily.

e. Responsible of data review.

The research team (PI and 2 co-investigators) will collect and analyze data.

f. Frequency of data review

Every week there will be a review of the cumulative data.

g. Conditions that trigger an immediate suspension of the research.

N/A

9. Withdrawal of Subjects

N/A

a. Anticipated circumstances under which subjects will be withdrawn from the research without their consent.

Patients will be withdrawn from the study if she develops an allergic or topical reaction to dressing or if the dressing has to be replaced due to soiling or bleeding.

N/A

b. Procedures for orderly termination.

N/A

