If during the preliminary data review one of the dressings is performing significantly better or worse than the others, or if one of the groups has higher incidence of catheter migration than that reported in the literature, the study will be terminated and the results analyzed up to that point.

c. Procedures that will be followed when subjects withdraw from the research

N/A

If there is withdrawal of consent or if a subject is withdrawn without consent for the circumstances cited above, those cases will be included in the analysis as "lost to follow-up" and reported in the results section.

10. Risks to Subjects

a. *Foreseeable risks.*

No risks additional to standard clinical care are foreseen. Topical or allergic reactions to the dressing materials would be managed by removal of the dressing and topical treatments.

b. *Costs that subjects may be responsible for because of participation in the research.*

N/A

N/A

c. *Risks to others who are not subjects.*

N/A

N/A

11. Potential Benefits to Subjects

There is no direct benefit to patients expected from their participation in this study. It is hoped the knowledge gained will be of benefit to other patients in the future.

12. Confidentiality

Procedures for maintenance of confidentiality.

See above

13. Consent Process

Before enrollment in the study, patients will be explained the purposes of the study, the risks and the procedures that will take place as part of the study. Time will be given to answer questions and PI contact information will be provided. Then, the patient will be given the opportunity to decide about participation in the study by signing the consent. The possibility of revoking the consent at any time during the study will also be explained (See consent form for details)..

14. Compensation for Research-Related Injury

This section is not required when research involves no more than Minimal Risk to subjects. **N/A**

a. *Describe the available compensation in the event of research related injury.*

N/A

15. Resources Available

N/A

a. *Availability of medical or psychological resources that subjects might need as a result of an anticipated consequences of the human research.*

N/A

b. *Process to ensure that all persons assisting with the research are adequately informed about the protocol, the research procedures, and their duties and functions.*

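### Section 9b obliges the team to end the trial on two triggers that cannot be applied as written: one leaves the 0.05 level unprotected, the other can cost planned power

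*Combined protocol and SAP*

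**What the plan says.** Section 9b (procedures for orderly termination) has two triggers. The first applies "If during the preliminary data review one of the dressings is performing significantly better or worse than the others". The second applies "if one of the groups has higher incidence of catheter migration than that reported in the literature, the study will be terminated". Either has the same mandatory consequence: "the study will be terminated and the results analyzed up to that point".

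The significance level appears only in the sample size statement (sections 4 and 7a): 35 patients per group for a 0.5 cm difference, with "a power of 90% and a statistical significance level of 0,05". No SD is given and interim looks are not mentioned.

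The primary outcome in section 7c is a signed distance: "Epidural catheter migration (ECM) in centimeters = Distance from tip to skin at insertion", minus the same distance at removal. No cut-off turns it into a yes/no event, and none of the five secondary outcomes is a migration incidence.

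On the timing of reviews, section 8b says "We will review the results for analysis at the end of data collection", while section 8f says "Every week there will be a review of the cumulative data". Section 8a provides "additional oversight from a Data and Safety Monitoring Committee" and concerns serious adverse events, unanticipated problems and reportable adverse events. Section 8g, on conditions for immediate suspension, reads N/A.

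**The concern.** A mandatory stopping rule is part of the trial's design, and its error rates depend on details that 9b leaves out.

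For the first trigger there is no test, outcome, boundary, number of looks or minimum sample. A second chance to declare significance at an unadjusted level raises the overall false-positive rate, and effects that cross the line early are on average too large.

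For the second trigger there is no event definition, reference value, margin or minimum sample. The background (section 2) offers figures for different events: 54% with no threshold stated and mostly inward, a similar figure outward in another study, and 13% inward with 22% outward by 1 cm or more in a third. Section 9b picks none. The team would have to choose both event and bar after seeing data, and could end a randomised comparison because one arm exceeded an outside figure. That can happen even when the three dressings perform alike, and it leaves too few patients for the planned comparison.

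**Working it through.** **Inputs from the documents:** three equal groups of 35, difference 0.5 cm, level 0.05, power 90%. **Assumed, because not stated:** two-sided tests, normal data, SD, look times, and 0.05 as the interim level.

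**1. The plan's own figure.** Without an SD, 35 per group cannot be reproduced forwards, so I solved for the SD. With n = 2(1.960 + 1.282)²(SD/0.5)² = 35, SD = 0.5 × √(35/21.0) = 0.645 cm. The exact t test gives 0.636. ANOVA gives 0.669 with one arm 0.5 cm apart and 0.579 with the third arm midway. The working range is therefore 0.58-0.67 cm, centred on 0.64.

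**2. Trigger 1, no true difference.** Simulated chance that the three-arm ANOVA gives p < 0.05 at any look, including the last (200,000 trials):

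| Looks, per arm | False-positive rate |
|---|---|
| 35 only | 5.0% |
| 18, 35 | 8.3% |
| 12, 24, 35 | 10.8% |
| 7, 14, 21, 28, 35 | 14.6% |

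With one interim, moving it to 10 or 25 per arm gives 8.9% or 7.5%.

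**3. Trigger 1, one arm truly 0.5 cm lower, one unadjusted look at 18 per arm, SD 0.64.** About 65% of trials stop early. The mean estimate among those is 0.60 cm (0.57-0.61 over the SD range); over all trials it is 0.53 cm. ANOVA power is about 92.6% with no look and about 93.4% with the look, so this trigger does not reduce power.

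**4. Trigger 2 as a point comparison, all arms exactly at the bar, 18 per arm.** P(stop) = 1 − P(X ≤ c)³, with X binomial(18, bar) and c the whole-number part of 18 × bar.

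- Bar 54%: 18 × 0.54 = 9.72, c = 9, one arm exceeds with probability 0.544; 1 − 0.456³ = 0.905.
- Bar 22%: 3.96, c = 3, 0.582; 1 − 0.418³ = 0.927.
- Bar 13%: 2.34, c = 2, 0.421; 1 − 0.579³ = 0.806.
- Bar 35% (13% + 22% summed): 6.3, c = 6, 0.451; 1 − 0.549³ = 0.834.

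For the first three bars, looks at 12 to 24 per arm give 76-93%. A one-sided exact test per arm (counts of 14, 8 and 6 of 18 or more) stops 7-10% at 18 per arm.

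**5. Trigger 2 away from the bar (bar 54%, 18 per arm).**

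| True incidence by arm | Point comparison | Exact test |
|---|---|---|
| 30/30/30% | 6% | under 0.1% |
| 30/30/50% | 43% | 1.6% |
| 30/30/60% | 75% | 9.4% |

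**6. Power at a truncated size.** Two-group t test, noncentrality (0.5/SD)√(n/2). At SD 0.636 and n = 18: 0.786 × 3 = 2.36 on 34 df, power 63% (59-71% over SDs 0.67 to 0.58). At n = 35: 0.786 × 4.18 = 3.29 on 68 df, power 90%. At 12 and 24 per arm it is 45% and 76%. These are unconditional: they describe a trial of that size, not a trial in which trigger 2 has fired.

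**7. An adjusted interim.** ANOVA p < 0.005 at 18 per arm, then p < 0.048 at 35: simulated overall error 5.0%.

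**The case against.** Several points on the other side have force.

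- *The interim level and number of looks are not stated.* True. A reader might infer from section 8f that significance is tested weekly, with error rates far above 14.6%. The documents do not support that: the weekly review may cover only safety or completeness, and 8b places review of results at the end. Only the direction is secure: any extra unadjusted look at 0.05 raises the error rate.
- *The test is assumed too.* One dressing against the others could mean pairwise tests. Unadjusted, these give about 12% with no interim look and about 20% with one, so much of that error is multiplicity, a separate matter. The ANOVA figures isolate the effect of looking.
- *Both triggers together.* A reader might infer that both harm level and power. They do not. Trigger 1 leaves power intact. With both active and the bar at the true rate, trigger 2 tends to end the trial at the first look and the ANOVA error stays near 5%, so the inflation belongs to trigger 1.
- *The 63% is not power given a trigger 2 stop.* Correct. Firing is related to arm differences; in illustrative settings conditional power ran from about 62% to 79%.
- *Near-certain stopping under trigger 2.* The 81-93% puts every arm at the bar. Section 5 of the working shows how far it falls otherwise.
- *The rule protects patients.* Both triggers cover a dressing doing worse, and section 8a does not clearly cover migration. Simply deleting them would lose that, so the fix must replace it.

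The N/A under the 9b heading is no answer; 9c carries the same mark above operative text.

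**Conclusion.** The concern holds and should be fixed before the rule is used. As written, 9b compels termination on a significance claim with no boundary, or on an undefined event compared with an unselected figure, and nothing elsewhere in the protocol supplies the missing pieces.

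The harms are distinct. Trigger 1 threatens the 0.05 level and the size of the reported effect; with one interim look the damage is moderate and grows with more looks, given unadjusted 0.05 and ANOVA. Trigger 2 threatens planned power by cutting the sample. How often it would fire is uncertain, from under 0.1% to 93% in the cases worked, depending on true incidence, the bar and the reading chosen. The effect-size and power figures rest on a back-solved SD of 0.58-0.67 cm.

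**What to change.** **Section 9b.** State that the study will not be stopped on an unadjusted between-group comparison of migration or on a direct comparison with published incidence. State that ECM will be compared among the three groups once, at 0.05, after the planned 35 per group have completed. Say whether that means randomised or evaluable patients, since 9a provides for withdrawals and section 3 excludes patients taken for cesarean section during the study.

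**If an early look is wanted.** One ANOVA at 18 per arm, run by the statistician, with p < 0.005, then p < 0.048 at the end.

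**Keeping watch for a worse dressing.** Turn the literature comparison into a prompt for review by the existing Data and Safety Monitoring Committee. State the reference, a matching event definition (added to 7c), a margin and a minimum number of patients.

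**Sections 8b, 8f and 9b.** Reconcile when, and for what purpose, cumulative data are reviewed.

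**Cost.** Wording only; no added patients or procedures. Automatic early stopping is given up for a worse as well as a better dressing, and 8a alone does not clearly fill that gap. The loss is small because section 6c describes all three dressings as current standard practice and committee review remains. The optional interim costs about 0.1-0.2 points of ANOVA power. Estimates from trials that stop there would still be too large (mean about 0.69 cm for a true 0.5 cm at SD 0.64) and should be reported with that caution.
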